Intervention and Mode of Delivery: If randomized to VOR/HCQ arm, we will administer VOR 400 mg PO daily and HCQ 600 mg PO daily in 4-week cycles. If randomized to RGF arm, we will administer RGF 160 mg PO daily for 3 weeks, of a 4-week cycle. Crossover to the other arm will be allowed, and is OPTIONAL, if the patient has disease progression or unacceptable toxicity. The option to get the crossover treatment will be left to the physician discretion, and if in the best interest of the patient.

Duration of Intervention and Evaluation: Follow-up: A repeat CT scan will be performed after 2 cycles of treatment regimen to evaluate response based on RECIST 1.1 criteria. CT scans will be repeated at least every 2 cycles, or 8 weeks, to ensure no progression of disease. Patients will continue VOR/HCQ or RGF until disease progression, unacceptable toxicity, withdrawal of consent by the patient, or decision of physician for patient's best interest. Crossover to the other arm will be allowed, but OPTIONAL, and will be determined by the treating physician for the patient's best interest. Each patient will be followed for 1 year. We will follow the last patient for 12 months, at which time, the study will be completed for data analysis.

Interim analysis: The O'Brien-Fleming procedure will be used to conduct an interim analyses for efficacy when 50% of the patients complete the study. A statistical basis for stopping the study at the first look will be achieved if the test statistic indicates benefit in the VOR/HCQ Arm and exceeds 2.96259, corresponding to a significance level of 0.003.

If the test statistic does not exceed 2.96259 at the first look then the trial will proceed to the final analysis. A treatment effect will be declared significant and beneficial at the final analysis if the test statistic indicates benefit and exceeds 1.96857, corresponding to a significance level of 0.047. If a treatment effect is not declared at the interim analysis, a statistical basis for stopping the study for futility will be attained if the conditional power is less than or equal to 20%.

Statistical Methods:

Analytic plan for primary objective:

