5.3 Treatment Requirements

All eligible patients who consent to this study must have a baseline evaluation (CT or MRI) within 6 weeks of the start of treatment.

Patient must meet all eligibility requirements to be entered onto the protocol.

5.3.1 Duration of Intervention and Evaluation:

Follow-up: A repeat CT scan will be performed after 2 cycles of treatment regimen to evaluate response based on RECIST 1.1 criteria (See Appendix 13.1 for definitions of response) (73). CT scans will be repeated at least every 2 cycles, or 8 weeks, to ensure no progression of disease. Patients will continue on VOR/HCQ or RGF until disease progression, unacceptable toxicity, withdrawal of consent by the patient, or decision of physician for patient's best interest. Crossover to the other arm will be allowed, but OPTIONAL, and will be determined by the treating physician for the patient's best interest. If patient is not given crossover treatment, then the patient will be off study and will be allowed to receive subsequent treatments. Each patient

will be followed for 1 year. We will follow the last patient for 12 months, at which time, the study will be completed for data analysis.

Interim analysis: The O'Brien-Fleming procedure will be used to conduct an interim analyses for efficacy when 50% of the patients complete the study. A statistical basis for stopping the study at the first look will be achieved if the test statistic indicates benefit in the VOR/HCQ Arm and exceeds 2.96259, corresponding to a significance level of 0.003. If the test statistic does not exceed 2.96259 at the first look then the trial will proceed to the final analysis. A treatment effect will be declared significant and beneficial at the final analysis if the test statistic indicates benefit and exceeds 1.96857, corresponding to a significance level of 0.047.

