- Biomarkers of efficacy of VOR/HCQ and RGF: We will obtain blood samples for plasma and PBMCs before start of treatment, prior to cycle 2, and off study treatment.

5.8 Biomarker Analysis.

Five blood samples will be collected during the timepoints listed above:

- Baseline (within 14 days of starting Cycle 1)
- Pre-Cycle 2
- Off Study Treatment

Blood samples will be collected in three tubes:

- Two - 10-ml EDTA tubes for plasma
- Three - 8 mL Vacutainer CPT tube for PBMCs

The blood samples will be processed, and stored at Pharmacokinetic Sampling Department (PSD), Institute of Drug Development, at the Cancer Therapy and Research Center.

Preparation of Plasma samples:

- 1) Collect 20 mL of whole venous blood into 2- 10 mL EDTA tubes
- 2) Centrifuge tubes at 2000 g for 15 minutes, at 4 C, to separate the cells from the Plasma.
- 3) Prepare the labels for the cryovials. The label for each tube should be written in black water fast ink.
- 4) Carefully transfer the top layer of the plasma from the EDTA tubes being careful not to disturb the Buffy Coat (white layer just below the plasma). Transfer up to 2 mL aliquots of plasma from the blood collection tubes into each of the 6 – 3.6 ml skirted bottom externally threaded cryovials.
- 5) Transfer the white thick layer above the red blood cell pellet from the blood collection tube into 2 – 2 ml cryovials.
- 6) Affix each label lengthwise to its corresponding tube and secure each label with a strip of clear plastic tape wrapped completely around the tube to ensure the label remains affixed to the tube during the freezing storage.
- 7) Immediately place the labeled tubes of plasma and buffy coat in an upright position in a 20°C freezer.
- 8) **Within 12 hours, transfer samples to -70°C freezer for long-term storage.**

Preparation of PBMC samples:

- Draw 8 mL of whole venous blood directly into each 8 mL Vacutainer CPT tubes and gently invert each tube 8 times.
- After inverting the tubes, centrifuge both tubes at room temperature at 1500-1 800 g (2800 rpm) for 20 minutes. NOTE: Centrifuge must be capable of generating at least 1500 RCF at the tube bottom.
- Draw off the clear plasma layer and discard, leaving behind cloudy PBMC layer lying just above the gel barrier.
- Transfer the PBMC layer into one 14 mL polypropylene centrifuge tubes.
- Add 10 mL of PBS-DEPC (at room temperature) to each tube and invert 3 to 4 times.
- Centrifuge at room temperature at 300 g (-1200 rpm) for 5 minutes.

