- Pour off and discard supernatant, leaving PBMC pellet behind.
- Cap tube and store at -20°C.
- **Within 12 hours, transfer samples to -70°C freezer for long-term storage.**

Tumor biopsy

At baseline, archival tissue from diagnosis will be documented, but if not available, we need documentation of mCRC. The archival tissue may be used for PD analysis. In such instances, TEN-FIFTEEN 15 micron (also called thick sections) paraffin-embedded tissue sections (unstained) and at least 1 H&E stained slide from the tumor biopsy.

Optional tumor biopsy may be done for accessible tumors at Cycle 2. If a patient cross-overs to the other therapy arm following progression, another optional biopsy may be performed at second cycle of crossover treatment. This allows for analysis of tumor cytotoxic effects of therapy.

Procedure for collection of Cycle 2 tumor biopsy:

2 cores will be obtained and sent to PK lab for analysis.

All planned PD analysis pertaining to the tumor biopsies obtained from patients with colorectal cancer, at baseline and again at 2 cycle (treatment arm or crossover arm) will be under supervision of the PI of the study.

6.0 Schedule of events:

Table 4: Study Calendar for Phase II study of VOR plus HCQ versus RGF in previously treated mCRC patients.

		Baseline (+/- 3 days)	Every cycle (+/- 3 days)	C1D15 and C2D15 only (+/- 3 days)	Every other cycle (+/- 3 days)	Pre-cycle 2 (+/- 3 days)	Off treatme nt (+/- 3 days)
Informed Consent^o	Xα						

History & Physical ✓	X€	X	Ω			X
Pathology review and KRAS status documentation ✓	X					
Vital Signs ✓	X	X				X
ECOG ✓	X	X				X
CBC, CMP ✓	X	X [^]	X ^Ω			X
CEA, ✓ LDH ✓	X	X [^]				X
PT/PTT ✓	X					
Serum Pregnancy Test °	X					
EKG ✓	X	X#			X#	
Tumor Evaluation (CTs)± ✓	X			X		X
Ophthalmologic Exam *°	X*					
Tissue biopsy °	X∞				X∞	
PBMCs & Plasma/Serum Biomarkers °¶	X				X	X
Adverse Events °%	X	X				X
Concurrent medication review °	Xf	X				X

✓ Standard of care

° Research purpose

α Consent should be done <30 days from C1D1, otherwise re-consent prior to C1D1

€ Baseline History and Physical should ask for porphyria since that is an exclusion criteria and make sure patient has not taken Regorafenib, hydroxychloroquine or vorinostat in the past. ^

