For Cycle 1, for patients who are assigned to VOR/HCQ arm, if baseline labs were done <14 days from C1D1, then can omit CBC, CMP, CEA and LDH. Upon randomization, regorafenib prescription will be sent to specialty pharmacy. If the patient receives the medication in <14

days, then the patient can start at home. This start date will be C1D1. If the patient receives ≥ 14 days, then the patient will need a C1D1 clinical visit and labs: CBC, CMP, CEA, LDH.

Repeat EKG after cycle 2 only if clinically relevant

Ω For Cycle 1 Day 15 and Cycle 2 Day 15, we will check CBC and CMP to evaluate for toxicity. Specifically, for RGF, we will monitor ALT, AST and bilirubin. For VOR, we will monitor blood counts. History and physical exam only as needed or if clinically indicated.

± Baseline CT should be Day -36 to Day -1. Every other cycle CT scans can be done +/- 4 days. Off treatment CT scan is done if not done at disease progression or in the last 28 days. (See Appendix 13.1 for definitions of response).

* ONLY required for patients receiving HCQ on study: If the patient is randomized to VOR/HCQ arm, and the patient is 70 year or older or has baseline ophthalmologic pathology (i.e., diabetic retinopathy), then a comprehensive eye exam will be done at baseline. If the

patient continues to receive HCQ on study at 6 months, a repeat comprehensive eye exam will be done at 6 months and then every 6 months while receiving HCQ on study. If the patient has visual disturbances while receiving HCQ, then an ophthalmologic evaluation will be done at that time. If the ophthalmologist recommends discontinuation of HCQ due to eye toxicity, then the patient will be taken off study for toxicity.

Patients receiving RGF are not required to have baseline or follow- up eye exams, unless there is crossover to the VOR/HCQ arm. If patient moves onto VOR/HCQ crossover arm, eye exam is as stated above (patient is 70 year or older or has baseline ophthalmologic).

∞ At baseline, archival tissue from diagnosis, but if not available, we need documentation of mCRC. Pre-cycle 2 tumor biopsy is optional. Follow instructions in **section 5.8.** ¶ Baseline should be done within 14 days of starting Cycle 1. Pre-cycle 2 and Off Treatment blood draws can occur +/- 3 days. Blood samples will be collected in five tubes: Two - 10-ml EDTA tubes for plasma, and Three - 8 mL Vacutainer CPT tubes for PBMCs. Follow instructions in **section 5.8.**

% NCI-CTCAE v4.0 will be used to document adverse events

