£ Patients should not have taken valproic acid or another histone deacetylase inhibitor for at least 2 weeks prior to enrollment.

BASELINE:

- HISTORY AND PHYSICAL
- PATHOLOGY REVIEW AND KRAS STATUS DOCUMENTATION
- VITAL SIGNS
- ECOG
- LABS: CBC, CMP, CEA, PT/PTT
- SERUM PREGNANCY TEST,
- PBMCS AND PLASMA BIOMARKERS
- EKG
- TUMOR EVALUATION (CT)
- OPHTHALMOLOGY EXAM - Baseline ophthalmologic evaluation to evaluate in patients randomized to VOR/HCQ ARM who are 70 years and older or have underlying eye disease.
- ADVERSE EVENTS EVALUATION
- CONCURRENT MEDICATION REVIEW

DAY 1 OF EVERY CYCLE

- HISTORY AND PHYSICAL EXAM
- VITAL SIGNS
- ECOG
- LABS : CBC, CMP
- EKG
- ADVERSE EVENTS EVALUATION
- CONCURRENT MEDICATION REVIEW

DAY 15 OF CYCLE 1

- LABS : CBC, CMP
- HISTORY AND PHYSICAL EXAM ONLY IF CLINICALLY INDICATED (AS NEEDED)

DAY 1 OF CYCLE 2

- HISTORY AND PHYSICAL EXAM
- VITAL SIGNS
- ECOG
- LABS : CBC, CMP
- PBMCS AND PLASMA BIOMARKERS
- EKG (Repeat EKG after cycle 2 only if clinically relevant)
- ADVERSE EVENTS EVALUATION
- CONCURRENT MEDICATION REVIEW

DAY 15 OF CYCLE 2

- LABS : CBC, CMP

- HISTORY AND PHYSICAL EXAM ONLY IF CLINICALLY INDICATED (AS NEEDED)

EVERY OTHER CYCLE

- TUMOR EVALUATION (CT)

DISEASE PROGRESSION:

- HISTORY AND PHYSICAL
- VITAL SIGNS
- ECOG
- LABS: CBC, CMP, CEA
- TUMOR EVALUATION (CT)
- ADVERSE EVENTS EVALUATION
- CONCURRENT MEDICATION REVIEW

OFF STUDY EVALUATION:

- HISTORY AND PHYSICAL
- VITAL SIGNS
- ECOG
- LABS: CBC, CMP, CEA, LDH
- PBMCS AND PLASMA BIOMARKERS
- TUMOR EVALUATION (CT) [if not done at disease progression or in last 28 days]
- ADVERSE EVENTS EVALUATION
- CONCURRENT MEDICATION REVIEW

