- Biomarkers of efficacy of VOR/HCQ and RGF: Biomarkers will be graphically displayed to demonstrate patterns across time and group and to identify the need for transformations and potential outliers. The significance of variation in biomarkers with treatment will be assessed with linear models with and without adjustment for age, sex, race and the baseline tumor KRAS status (mutated, wild type). The dependent variables will be log transformed (base 2) if necessary. The relation between treatment efficacy, as measured by PFS-1, and biomarkers will be assessed with proportional hazards models in terms of treatment, the biomarker, the biomarker by treatment interaction, age, sex, race, and baseline tumor K-RAS status (mutated, wild type). Significant effects will be described and illustrated, as appropriate, with Kaplan Meier plots by strata determined by biomarker level and treatment group, for example.

Sample size justification: Historically, the mPFS for previously treated mCRC patients treated with RGF is 1.9 mos. We predict VOR/HCQ will improve mPFS to 3.8 months. We expect 5% lost to follow-up. Assuming a 36-month accrual period with 1 year for follow up, 36 subjects per group are necessary to obtain 80% power. With 5% lost to follow-up the sample size required per group is 38 ($=36/0.95$), therefore, the total required sample size is 76 subjects. As a result, the target accrual rate is 3-4 patients/month to achieve a target accrual at 36 months with an additional 12-month follow-up.

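### For patients who cross over, the visit lists place the third blood biomarker sample after the other arm's drug, so a comparison by randomised arm at that time point would be diluted

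*Combined protocol and SAP*

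**What the plan says.** Identifying biomarkers associated with efficacy of each regimen is a secondary objective (Section 3.0). Section 5.7 sets the sampling: "We will obtain blood samples for plasma and PBMCs before start of treatment, prior to cycle 2, and off study treatment". Section 5.8 repeats the three time points. The Table 4 footnote calls the last one by another name: "Pre-cycle 2 and Off Treatment blood draws can occur +/- 3 days".

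The visit lists that follow Table 4 carry the item "PBMCS AND PLASMA BIOMARKERS" under Baseline, Day 1 of Cycle 2 and Off Study Evaluation. The separate Disease Progression list does not carry it.

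On crossover, the Synopsis (Intervention and Mode of Delivery) states: "Crossover to the other arm will be allowed, and is OPTIONAL, if the patient has disease progression or unacceptable toxicity". Section 5.3.1 says when a patient leaves the study after the first regimen: "If patient is not given crossover treatment, then the patient will be off study and will be allowed to receive subsequent treatments". Crossover has its own text for tissue in Section 5.8 ("another optional biopsy may be performed at second cycle of crossover treatment") and for eye examinations in the Table 4 footnotes. It has none for blood biomarkers.

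On analysis, Section 10.0 states: "Biomarkers will be graphically displayed to demonstrate patterns across time and group". It adds linear models for the variation of markers with treatment, and proportional hazards models relating markers to PFS-1. It does not say which time points enter these models or how samples taken after crossover are handled.

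**The concern.** A patient who crosses over stays on study. If the third draw belongs to the Off Study Evaluation, that patient is sampled after the second regimen, whereas a patient who does not cross over is sampled after the randomised one. Within each randomised arm, the third time point would then hold a mixture of samples following VOR/HCQ and samples following RGF.

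The mixing matters because Section 2.6.1 expects VOR/HCQ to move specific markers: CTSD, CDKN1A and SQSTM1/p62 up, HMGB and RAGE down. On that hypothesis, RGF patients who cross over would bring the VOR/HCQ pattern into the RGF arm, and VOR/HCQ patients who cross over would do the reverse.

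The analysis cannot fully repair this. A value not sampled before crossover cannot be recovered. Dropping crossover patients selects after randomisation, because crossover is at the physician's discretion.

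**Working it through.** **Where the draws fall (Section 6.0 visit lists)**

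| Visit list | Biomarker blood | Routine blood |
|---|---|---|
| Baseline | yes | yes |
| Day 1 of Cycle 2 | yes | yes |
| Disease Progression | no | CBC, CMP, CEA |
| Off Study Evaluation | yes | CBC, CMP, CEA, LDH |

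Read with Section 5.3.1, this gives two sequences. Without crossover: baseline, pre-cycle 2, end of randomised drug. With crossover: baseline, pre-cycle 2, then nothing until after the other arm's drug. The same gap arises when crossover follows unacceptable toxicity.

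**The plan's own figure.** No sample size is given for the biomarker objective. The PFS-1 figure can be reproduced. The hazard ratio is 1.9/3.8 = 0.50. With 80% power and an assumed two-sided 0.05, Freedman's formula gives 71 events. The mean event probability over 36 months' accrual plus 12 months' follow-up is 0.991 under exponential survival. Then 71/0.991/2 = 35.8, so 36 per arm, and 36/0.95 gives 38. I use 38 per arm below, ignoring attrition.

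**Dilution.** Let a and b be the mean marker values after each drug, and cA and cB the crossover shares. Assume the third sample reflects only the drug last taken.

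- Arm A mean: (1 − cA)a + cA·b
- Arm B mean: (1 − cB)b + cB·a
- Difference: (1 − cA − cB)(a − b)

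The documents give no crossover rate, so the table shows a range with equal shares c. The true difference is an assumed 0.65 SD with two-sided 0.05. Power is Φ(δ√(n/2) − 1.96), where δ is the expected contrast in SD units and the SD is held fixed.

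| c in each arm | Factor 1 − 2c | Power, all patients by arm | Non-crossover patients per arm, 38(1 − c) | Power, non-crossover only |
|---|---|---|---|---|
| 0 | 1.0 | 0.81 | 38 | 0.81 |
| 0.1 | 0.8 | 0.62 | 34.2 | 0.77 |
| 0.2 | 0.6 | 0.40 | 30.4 | 0.72 |
| 0.3 | 0.4 | 0.20 | 26.6 | 0.66 |
| 0.4 | 0.2 | 0.08 | 22.8 | 0.59 |
| 0.5 | 0 | no expected contrast | 19.0 | 0.52 |

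Worked row, c = 0.2: δ = 0.6 × 0.65 = 0.39; 0.39 × √19 = 1.70; Φ(1.70 − 1.96) = 0.40.

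**Sensitivity to residual effect.** If half of the first drug's effect remains in the crossover patient's sample, the factor is 1 − 2c × 0.5 = 1 − c. At c = 0.2 this is 0.8, with power 0.62 instead of 0.40. The loss is smaller but still present.

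**With a draw before crossover.** The patients whose third sample follows only the randomised drug rise from 38(1 − c) to 38 per arm. The smallest difference detectable with 80% power, 2.80 × √(2/n), goes from 0.72, 0.83 and 1.02 SD at c = 0.2, 0.4 and 0.6 to 0.64 SD.

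**The case against.** The best counter-argument is that the timing is ambiguous, not wrong. Sections 5.7 and 5.8 and Table 4 speak of coming off treatment; only the visit list speaks of coming off study. Table 4 has no progression column, so its last column could be read as the end of whichever regimen the patient is on. The scan footnote ("Off treatment CT scan is done if not done at disease progression or in the last 28 days") fits a visit close to progression. Nothing says whether the calendar restarts at crossover. This stands in part: a site could sample at the end of the first regimen. But the separate Disease Progression list, without the draw, points the other way, and if sites read the labels differently, samples from different points would be pooled.

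Second, the arithmetic is conditional. It rests on an unstated crossover rate, on the sample reflecting only the last drug, and on an analysis by randomised arm at the third time point, which Section 10.0 neither specifies nor excludes. This stands: the table shows sensitivity and forecasts nothing.

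Third, the markers are meant to predict efficacy, and baseline and pre-cycle 2 values serve that. The first scheduled response scan comes after two cycles, so most crossover for radiographic progression would come after the pre-cycle 2 draw. This also stands. A reader might infer that a progression sample is needed to relate markers to PFS-1. It is not, because a value taken at the PFS-1 event cannot predict that event. Resistance and the crossover drug's own effect on markers are not stated biomarker objectives either.

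**Conclusion.** The concern holds for patients who cross over. As the visit lists and Section 5.3.1 read, their third blood sample follows the other arm's drug and no sample precedes the first crossover dose; the differing labels elsewhere leave the intended timing unclear. A comparison by randomised arm at the third time point would be diluted by the factor 1 − cA − cB if the sample reflects only the last drug, and by less if the first drug's effect persists.

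A reader might go further and infer that the third time point cannot show the effect of randomised treatment at all, or that the biomarker objective fails. The documents do not support that. Patients who do not cross over are sampled after the randomised drug, and the baseline and pre-cycle 2 samples come before crossover in everyone who reaches cycle 2 on the randomised drug. Nor is there a basis for expecting the contrast to reverse: that needs cA + cB above 1, and no crossover rate is given. The primary analysis and the total of 76 patients are untouched.

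**What to change.** In Sections 5.7 and 5.8, Table 4 and the visit lists of Section 6.0, use one term for the third draw. Define it as the PBMC and plasma sample taken at the end of the randomised regimen, whether that ends for progression or toxicity, and before any crossover dose. Add it to the Disease Progression list.

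In Section 10.0, name this sample as the third time point in the biomarker analyses by randomised group. State that samples taken after a crossover dose stay out of that comparison; if kept, they belong in a separate crossover analysis with the end-of-regimen sample as baseline.

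The cost is small. Blood is already taken at the progression visit, so for crossover patients the draw moves to an earlier visit. Keeping the post-crossover sample as well is optional and adds one five-tube set per crossover patient: 2 × 10 mL + 3 × 8 mL = 44 mL. No sample size, dose or clinical rule changes.

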In refractory mCRC, the role of VEGF inhibition in mCRC patients has not been established (30). Recently, Regorafenib (RGF), an oral multi-kinase inhibitor, including with angiogenic inhibition, was approved for mCRC patients who have failed standard therapies (2). In the CORRECT trial, patients with mCRC were randomized in a 2:1 ratio to receive best supportive care with oral RGF 160 mg or placebo by mouth once daily, for 3 weeks of a 4-week cycle (3). The primary endpoint was overall survival. *Compared to placebo, RGF improved mPFS from 1.7 to 1.9 months ($P<0.000001$) and mOS from 5.0 to 6.4 months ($P=0.005$), regardless of K-RAS status (3).* The most common treatment-related toxicities were fatigue (47% vs 28%, RGF vs placebo), hand-foot syndrome (47% vs 8%), diarrhea (34% vs 8%), anorexia (30% vs 15%), voice changes (29% vs 6%), hypertension (28% vs 6%), oral mucositis (27% vs 4%), rash/desquamation (26% vs 4%), nausea (14% vs 11%), weight loss (14% vs 2%), and fever (10% vs 3%). In this study, 54% patients had grade 3 or more adverse events versus 14% with placebo, with the most common grade 3 fatigue (9% vs 5%) and grade 3 hand-foot syndrome (17% vs <1%). In the third-line setting, even when statistical significance is reached, gains in PFS and OS are modest, i.e., 0.2 months (6 days) improvement in mPFS and the 1.4 months (42 days) benefit in mOS seen with RGF over placebo (3). Given the modest improvements of RGF in survival, VEGF inhibition may not be beneficial to all patients with mCRC refractory to VEGF inhibitors; therefore, more therapies are needed in patients with mCRC progressing despite VEGF inhibition.

2.3 Autophagy as a mechanism for cancer survival:

Autophagy is a conserved protein degradation process that involves the vacuolar sequestration of long-lived cytoplasmic proteins and organelles into a structure called an autophagosome (31).

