- Inform patients to store medicine in the original container. Do not place medication in daily or weekly pill boxes. Any remaining tablets should be discarded 28 days after opening the bottle. Tightly close bottle after each opening and keep the desiccant in the bottle

Known Potential Toxicities of Regorafenib:

Hepatotoxicity: Severe drug induced liver injury with fatal outcome occurred in 0.3% of 1200 Stivarga-treated patients across all clinical trials. Liver biopsy results, when available, showed hepatocyte necrosis with lymphocyte infiltration. In Study 1, fatal hepatic failure occurred in 1.6% of patients in the Regorafenib arm and in 0.4% of patients in the placebo arm; all the patients with hepatic failure had metastatic disease in the liver. In Study 2, fatal hepatic failure occurred in 0.8% of patients in the Regorafenib arm. Obtain liver function tests (ALT, AST and bilirubin) before initiation of Stivarga and monitor at least every two weeks during the first 2 months of treatment. Thereafter, monitor monthly or more frequently as clinically indicated. Monitor liver function tests weekly in patients experiencing elevated liver function tests until improvement to less than 3 times the ULN or baseline. Temporarily hold and then reduce or permanently discontinue Stivarga depending on the severity and persistence of hepatotoxicity as manifested by elevated liver function tests or hepatocellular necrosis.

>10%:

Cardiovascular: Hypertension (30% to 59%; grade ≥ 3 : 8% to 28%)

Central nervous system: Fatigue (52% to 64%), dysphonia (30% to 39%), pain (29%), fever (21% to 28%), headache (10% to 16%)

Dermatologic: Palmar-plantar erythrodysesthesia (45% to 67%; grade ≥ 3 : 17% to 22%), rash (26% to 30%; grade ≥ 3 : 6% to 7%), alopecia (8% to 24%)

Endocrine & metabolic: Hypocalcemia (17% to 59%), hypophosphatemia (55% to 57%), hyponatremia (30%), hypokalemia (21% to 26%), hypothyroidism (4% to 18%)

Gastrointestinal: Appetite decreased (31% to 47%), lipase increased (14% to 46%), diarrhea (43% to 47%), mucositis (33% to 40%), weight loss (14% to 32%), amylase increased (26%), nausea (20%), vomiting (17%)

Hematologic: Anemia (79%; grade 3: 5%; grade 4: 1%), lymphopenia (30% to 54%; grade 3: 8% to 9%), thrombocytopenia (13% to 41%; grade 3: 1% to 2%; grade 4: <1%), INR increased (24%), hemorrhage (11% to 21%; grade ≥ 3 : 2% to 4%), neutropenia (3% to 16%; grade 3: 1% to 2%)

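### The study calendar has no scheduled blood-pressure reading on days 5-21 of the regorafenib (RGF) course, and a home start may leave the first course with none; adding vital signs at Day 15 is a cheap repair

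*Combined protocol and SAP*

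**What the plan says.** Table 4 (Section 6.0) marks vital signs at baseline, every cycle (+/- 3 days) and off treatment. The visit lists agree: vital signs appear at baseline, under "DAY 1 OF EVERY CYCLE" and again at Cycle 2 Day 1, at progression and off study. The column for Day 15 of Cycles 1 and 2 (+/- 3 days) has CBC and CMP. Footnote Ω adds "History and physical exam only as needed or if clinically indicated", and the Day 15 lists repeat this. The adverse-event row is also blank at Day 15.

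On dosing, the Synopsis states "we will administer RGF 160 mg PO daily for 3 weeks, of a 4-week cycle". On starting RGF, Section 5.2 and footnote ^ of Table 4 say that if the drug arrives in under 14 days, "then the patient can start at home. This start date will be C1D1". A C1D1 clinic visit is required only if it arrives at 14 days or later.

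On blood pressure itself:

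- Section 5.4.3 interrupts RGF for symptomatic Grade 2 hypertension and for any Grade 3 or 4 reaction.
- Section 5.6.3 (Patient Care Implications) says patients should be told that their blood pressure will need monitoring, and that they should make contact if it is raised or if symptoms occur. It gives no frequency.
- Section 5.4.3 does give a frequency for liver tests: at least two-weekly for the first 2 months.

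**The concern.** Hypertension is a common, expected and dose-modifying toxicity of RGF, and it can be present without symptoms: the interruption rule itself singles out the symptomatic form of Grade 2. Liver toxicity has a mid-course check that the Day 15 blood draw delivers. Blood pressure has none in the calendar, although the same time point could serve.

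The as-needed examination at Day 15 is a weak substitute. With no adverse-event review or vital signs scheduled that day, it depends on the patient reporting something or on the blood results, and neither CBC nor CMP measures blood pressure. Raised pressure without symptoms may then be found only at the next Day 1, when that 21-day course is finished and none of its doses can be held. What is at stake is patient safety and timely dose modification, not the efficacy analysis.

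**Working it through.** **Inputs.** RGF dosing on days 1-21 of a 28-day cycle (Synopsis; Section 5.3.3). Vital signs on Day 1 +/- 3 days, Day 15 blood tests +/- 3 days (Table 4). 38 patients per arm, 76 in all (Section 5.1). RGF hypertension 30% to 59% of any grade and 8% to 28% grade 3 or higher (Section 5.6.3); 28% on RGF against 6% on placebo in the phase III trial (Section 2.2.1). The plan states no figure of its own to reproduce here.

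**Calendar as written, clinic start.** The Day 1 window closes on day 1 + 3 = 4. The next opens on day 29 - 3 = 26. Dosing days on which no scheduled reading can fall: 5 to 21, which is 17 of 21 (81%).

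**Calendar as written, home start without a C1D1 visit.** The first on-treatment reading is at C2D1, days 26 to 32. No dosing day of Cycle 1 can hold a scheduled reading: 21 of 21. That reading comes 26 - 21 = 5 to 32 - 21 = 11 days after the last dose of the course.

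**With vital signs at Day 15.** The window is 15 +/- 3 = days 12 to 18, which is 7 days.

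| Dosing days on which no scheduled reading can fall | As written | With Day 15 |
|---|---|---|
| Clinic start, Cycles 1 and 2 | 17 of 21 | 17 - 7 = 10 of 21 (days 5-11 and 19-21) |
| Home start, Cycle 1 | 21 of 21 | 21 - 7 = 14 of 21 |
| Cycle 3 onward | 17 of 21 | 17 of 21 |

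These are days on which a visit could be placed, not days under observation. Each visit gives one reading, so the real gain is one added reading in each of two cycles.

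**Timing for a home start.** The first on-treatment reading comes earlier by 26 - 18 = 8 to 32 - 12 = 20 days (29 - 15 = 14 nominal). Doses left after the visit-day dose: 21 - 18 = 3 to 21 - 12 = 9. At C2D1, none of that course remain.

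**Expected hypertension among 38 RGF patients.**

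- Any grade, Section 5.6.3: 0.30 x 38 = 11.4 to 0.59 x 38 = 22.4.
- Any grade, phase III rate: 0.28 x 38 = 10.6, against 0.06 x 38 = 2.3 at the placebo rate.
- Grade 3 or higher: 0.08 x 38 = 3.0 to 0.28 x 38 = 10.6.

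The last line is the more relevant one for holding RGF, because every Grade 3 or 4 reaction requires interruption. All are expected totals, not numbers found late.

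**Cost.** 2 x 76 = 152 added readings at most on the first regimen, plus at most 2 for each patient who crosses over.

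**The case against.** The strongest reply is that the calendar sets minimum study readings and is not the whole of monitoring. Section 5.6.3 says RGF patients will need blood-pressure monitoring and should report raised pressure with or without symptoms. Vital signs are tagged standard of care in Table 4, so staff may take them at a Day 15 visit anyway. The RGF handout (Section 5.3.3, Appendix 12.3) is not in the available text and may give home blood-pressure advice. Section 8.0 breaks off where it begins to describe what happens at each visit. This stands, and it confines the point to the calendar. A reader might infer that the protocol provides no blood-pressure monitoring on RGF, or sets no frequency anywhere; the available text cannot support that. None of these sources, as far as they can be seen, puts a mid-course reading in Table 4 or the Day 15 lists.

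The home-start gap is also partly inference. Footnote ^ is attached to the laboratory rows, and the Day 1 list has no home-start exemption, so Day 1 vital signs are not expressly waived. But requiring a C1D1 clinic visit only when the drug arrives late suggests that there is otherwise none. Hence may, not will.

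Finally, progression or off-study visits, or an as-needed examination, can fall on days 5-21 by chance. They are not scheduled mid-course readings.

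**Conclusion.** The point holds for the calendar. No scheduled on-treatment blood-pressure reading can fall on days 5-21 of an RGF course, and a patient who starts at home may have none in the whole first course. This should be changed, as a cheap safety improvement; it is not a flaw in the analysis.

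Two stronger inferences are not supported. One is that 11 to 22 patients would have their hypertension missed: that is the expected total of any grade, and silent Grade 1 or 2 would not trigger a hold under Section 5.4.3. Even for the 3 to 11 with grade 3 or higher, the documents do not say how many would be silent, so the number found late cannot be computed. The other is that efficacy results are at risk: nothing here touches the PFS-1 analysis.

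The conclusion rests on the visits falling within their stated windows, on 38 patients in the RGF arm, and on the toxicity rates that the protocol quotes. Confidence is medium because of the unavailable text.

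**What to change.** In Table 4 and in both Day 15 lists, add vital signs (blood pressure) at C1D15 and C2D15, in both arms and on the same days of a crossover regimen. Leave all dose thresholds as they are. Both arms are included so that neither gets more readings than the other.

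The change is two calendar marks, two lines in the visit lists and one CRF entry per time point. The burden is a few minutes of staff time per reading. There is no extra visit if Day 15 blood is drawn at the study clinic; Section 6.0 does not say where it is drawn, and a clinic reading would be needed if it is drawn elsewhere. VOR/HCQ patients gain little themselves, since Section 5.6.2 lists hypertension for vorinostat among events under 1%. Days 5-11 and 19-21 of Cycles 1 and 2, and days 5-21 of later cycles, would still have no scheduled reading.
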